5.6 Duration of Follow-Up

Participants will follow-up at approximately 4 weeks for an end of study clinic visit after the last dose of study drug whenever possible. If an in-person visit is not possible, the participant will be contacted by phone. Immune mediated event surveillance will be conducted approximately 100 days after the last dose of study treatment via telephone. Otherwise, ongoing long-term follow-up will be accomplished by phone for all participants. Participants will be followed approximately every three months until death.

In addition to the follow-up schedule above, participants removed from protocol therapy for unacceptable adverse event(s) will be followed until resolution or stabilization of the adverse event.

In participants who come off trial for a reason other than progressive disease, if possible during the follow-up period, scans should be performed every 8 weeks or 2 months to evaluate for disease progression, until the participant has disease progression or dies or starts a new systemic therapy.

NOTE: With Protocol Version 15MAY2024, further long-term follow-up is being terminated.

5.7 Criteria for Taking a Participant Off-Study

Participants will be removed from study when any of the following criteria apply:

- Lost to follow-up
- Withdrawal of consent for data submission
- Death
- Inability to follow study protocol as listed in section 5.6.

The reason for taking a participant off study and the date the participant was removed must be documented in the CRF.

For Decentralized Participant Registrations, the research team updates the relevant Off Treatment/Off Study information in OnCore.

5.8 Criteria to Resume Treatment after a pembrolizumab related iAE

Management of adverse events is summarized in section 6 and may include holding of pembrolizumab, and/or the use of steroids for the management of immune related AEs. If pembrolizumab is held for toxicity, participants are permitted to continue protocol therapy with eribulin. Eribulin can be continued during corticosteroid treatment.

If drug administration is held until the next scheduled time point, please continue to count weeks/doses. If participants must be delayed due to toxicity, all assessments can be obtained with the modified treatment dose schedule as noted in this section.

Pembrolizumab may be interrupted for situations other than treatment-related AEs such as medical / surgical events or logistical reasons not related to study therapy. Participants should be placed back on study therapy within 8 weeks of the scheduled interruption, unless otherwise discussed with the Sponsor. The reason for interruption should be documented in the participant's study record.

Restarting pembrolizumab may be considered in participants who experience grade 2 events and some grade 3 events (skin rash and thyroiditis). Because of this, stopping treatment and starting steroids earlier, as per section 6, to obtain resolution with the possibility for restarting rather than waiting for higher grade events is encouraged.

For non-autoimmune or non-inflammatory events, participants may resume treatment with study drug when the drug-related AE(s) resolves to Grade ≤ 1 or the baseline value, with the following exceptions:

- Evaluation to exclude any additional immune mediated events (endocrine, GI, and liver / pancreas function) as clinically indicated must be made prior to restarting. [SEP]
- Non-drug-related toxicity including hepatic, pulmonary toxicity, diarrhea, or colitis, must have resolved to baseline before treatment is resumed. [SEP] If the criteria to resume treatment are met, the participant should restart treatment no sooner than the next scheduled time point per protocol. However, if the treatment is delayed past the next scheduled time point per protocol, the treatment should resume at the earliest convenient point [SEP] that is within the five-week delay period.

For participants treated with corticosteroids:

For participants treated with high dose steroids with pembrolizumab, toxicity must resolve to baseline within 8 weeks of treatment.

Participants should be off steroids for at least 2 weeks with no recurrence or new events. New immune related events or exacerbation of existing events during steroid treatment or taper suggest the presence of ongoing immune activation and should require permanent discontinuation of pembrolizumab.

Grade 2 events must resolve to grade < 1 or baseline before considering retreatment.

All participants treated with steroids for grade ≥ 2 events should have pembrolizumab held until resolution to grade < 1 for at least 2 weeks following complete removal from steroid treatment except for maintenance replacement doses for adrenal insufficiency (preferably no greater than 10mg prednisone equivalent daily).

All participants treated with steroids for grade ≥ 3 events should have pembrolizumab discontinued. Participants with grade 3 thyroiditis and skin rash may continue therapy as for grade 2 events with resolution and stable replacement treatment.

Participants with hepatitis, pancreatitis, pneumonitis, and colitis are at risk for exacerbation with retreatment if there is residual inflammation and should resolve to Grade 0 or baseline before retreatment. Baseline can mean the initial grade *i.e.* grade ≤ 1 where permitted on study.

Participants with thyroiditis or hypopituitarism who are stable as above may be restarted with replacement hormones including thyroid hormone and physiologic doses only of corticosteroids. Please note that hypophysitis with symptoms of headache, visual or neurologic changes or radiologic evidence of pituitary enlargement and other CNS events such as aseptic meningitis or encephalitis should be considered grade 3 events.

Prior to starting corticosteroids or hormone replacement for any reason, appropriate endocrine testing including cortisol, ACTH, TSH and T4 must be drawn if clinically feasible to document baseline function and distinguish the pituitary from peripheral organ dysfunction and later from steroid (or thyroid) treatment associated ACTH (or TSH) suppression. Steroids should be started prior to obtaining results based on clinical indications.

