5.2.3 Day 1 of subsequent cycles

Criteria to treat on Day 1 of subsequent cycles:

- Absolute neutrophil count $>1000/\text{mcL}$
- Platelets $>100,000/\text{mcL}$
- ALT and AST $<2.5 \times \text{ULN}$ in a participant with no documented liver metastases; ALT and AST $<5.0 \times \text{ULN}$ in a participant with documented liver metastases
- Total bilirubin $<1.5 \times \text{ULN}$ ($2.0 \times \text{ULN}$ in a participant with well documented Gilbert's syndrome)

Any non-hematologic toxicities must return to baseline or to $< \text{Grade } 2$ beginning with Day 1 of each cycle.

If dose is held or missed on Day 1 of a cycle, that cycle will not be considered to start until the day the dose is actually administered to the patient (ie, D1-D8-rest, X-D1-D8-rest, etc.)

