5.5 Duration of Therapy

Duration of therapy will depend on individual response, evidence of disease progression and tolerance. In the absence of treatment delays due to adverse event(s), treatment may continue for 2 years or 35 cycles of therapy or until one of the following criteria applies:

- Disease progression in any participant who showed first radiologic evidence of progressive disease (PD) by RECIST 1.1 (see Section 11.1.4) and is deemed clinically stable, it is at the discretion of the investigator to continue treating the participant until progression is confirmed at least 4 weeks from the date of the first radiologic evidence of PD. Further details are described below.
- Intercurrent illness that prevents further administration of treatment
- Unacceptable adverse event(s) which include the following (see also section):
 - Any Grade 2 drug-related uveitis or eye pain or blurred vision that does not respond to topical therapy and does not improve to Grade 1 severity within the re-treatment period OR requires systemic treatment
 - Participants requiring > two dose delays for the same type of event should be removed from protocol
 - Any adverse event, laboratory abnormality, or intercurrent illness which, in the judgment of the investigator, presents a substantial clinical risk to the participant with continued study drug dosing
 - Any dosing interruption lasting >5 weeks, with the following exceptions:
 - Participants being tapered after high dose corticosteroids over one month followed by a two-week observation period will be allowed an additional two weeks to restart treatment (a maximum eight-week interruption).
 - Dosing interruptions >5 weeks that occur for non-drug-related reasons may be allowed if approved by the Investigator. Prior to re-initiating treatment in a participant with a dosing interruption lasting >5 weeks, the PI must be consulted.
 - Grade 2 pneumonitis requiring steroids.
 - Grade 3 or Grade 4 drug-related autoimmune or inflammatory events including uveitis, pneumonitis, diarrhea, colitis, neurologic adverse events, hypersensitivity reaction, or infusion reaction of any duration requires discontinuation except as noted below:
 - Any other grade 3 non-skin, drug-related AE lasting >7 days including fatigue.

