General instructions: 
 1. Corticosteroid taper should be initiated upon AE improving to Grade 1 or less and continue to taper over at least 4 weeks. 2. For situations where pembrolizumab has been withheld, pembrolizumab can be resumed after AE has been reduced to Grade 1 or 0 and corticosteroid has been tapered. Pembrolizumab should be permanently discontinued if AE does not resolve within 12 weeks of last dose or corticosteroids cannot be reduced to ≤ 10 mg prednisone or equivalent per day within 12 weeks. 3. For severe and life-threatening irAEs, IV corticosteroid should be initiated first followed by oral steroid. Other immunosuppressive treatment should be initiated if irAEs cannot be controlled by corticosteroids. 				
Immune-related AEs	Toxicity grade or conditions (CTCAEv5.0)	Action taken to pembrolizumab	irAE management with corticosteroid and/or other therapies	Monitor and follow-up
Pneumonitis	Grade 2	Withhold	
 • Administer corticosteroids (initial dose of 1-2 mg/kg prednisone or equivalent) followed by taper 	
 • Monitor participants for signs and symptoms of pneumonitis • Evaluate participants with suspected pneumonitis with radiographic imaging and initiate corticosteroid treatment • Add prophylactic antibiotics for opportunistic infections
	Grade 3 or 4, or recurrent Grade 2	Permanently discontinue		
Diarrhea / Colitis	Grade 2 or 3	Withhold	
 • Administer corticosteroids (initial dose of 1-2 mg/kg prednisone or equivalent) followed by taper 	
 • Monitor participants for signs and symptoms of enterocolitis (ie, diarrhea, abdominal pain, blood or mucus in stool with or without fever) and of bowel perforation (ie, peritoneal signs and ileus). • Participants with \geq Grade 2 diarrhea suspecting colitis should consider GI consultation and performing endoscopy to rule out colitis. • Participants with diarrhea/colitis should be advised to drink liberal quantities of clear fluids. If sufficient oral fluid intake is not feasible, fluid and electrolytes should be substituted via IV infusion.
	Grade 4	Permanently discontinue		

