Grade 2	Continue at investigator discretion
Grade 3	Hold until ≤ Grade 1. Resume at same dose level at investigator discretion.
Grade 4	Stop pembrolizumab
Participants with fever should be evaluated as clinically appropriate. Participants may experience isolated fever during infusion reactions or up to several days after infusion. Evaluation over the course of 1-2 weeks should be done for other autoimmune events that may present as fever	
See section 5.10: Treatment of Pembrolizumab Infusion reactions	

If treatment is delayed >8 weeks for an adverse event, the participant must be permanently discontinued from study therapy.

Participants requiring high dose steroid treatment for autoimmune or inflammatory events should be managed as described in section 5.9, except for a short course of tapering steroids for infusion reaction, skin rash, or endocrine events.

Participants with grade 3 thyroiditis and skin rash may continue therapy as for grade 2 events with resolution and stable replacement treatment.

Participants with thyroiditis or hypopituitarism who are stable as above may be restarted with replacement hormones including thyroid hormone and physiologic doses of corticosteroids. Please note that grade for hypophysitis with symptoms of headache, visual, or neurologic changes or radiologic evidence of pituitary enlargement and other CNS events such as aseptic meningitis or encephalitis should be considered grade 3 events.

Any participant who requires additional immune suppressive treatment beyond steroids should stop pembrolizumab.

Participants requiring > two dose delays, other than for evaluation for the same event, should stop pembrolizumab. Participants may be dose-delayed for evaluation and restarted depending on results.

Prior to starting corticosteroids or hormone replacement for any reason, appropriate endocrine testing including cortisol, ACTH, TSH and T4 must be obtained to document baseline.

Please note that in some cases the treatment algorithms recommend steroids if symptoms do not resolve in 7 days. However, this recommendation is not meant to delay steroid treatment at any time it is clinically indicated.

Any participant started on corticosteroids initially who is determined to not require steroids treatment for an autoimmune adverse event may resume therapy after a 2-week observation period without further symptoms at the discretion of the PI or investigator.

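### Table 4.1 lets pembrolizumab restart after a steroid-treated Grade 2 immune-related event without the two steroid-free weeks in Section 5.8, and Section 6 cites the wrong section for that rule

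*Combined protocol and SAP*

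**What the plan says.** **Section 5.8** holds the resumption criteria. After steroids for an event of Grade 2 or higher, participants "should have pembrolizumab held until resolution to grade < 1 for at least 2 weeks following complete removal from steroid treatment"; the exception is maintenance replacement for adrenal insufficiency. It separately asks for two weeks off steroids without recurrence or new events. Participants with hepatitis, pancreatitis, pneumonitis or colitis "are at risk for exacerbation with retreatment if there is residual inflammation and should resolve to Grade 0 or baseline before retreatment", where baseline may be Grade 1 or less if that was allowed at entry.

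**Table 4.1 (Section 6.2)**, general instruction 1, starts the steroid taper when the event improves to Grade 1 or less and runs it for at least 4 weeks. Under instruction 2, "pembrolizumab can be resumed after AE has been reduced to Grade 1 or 0 and corticosteroid has been tapered". The only steroid dose it names is in its stopping rule, which applies when "corticosteroids cannot be reduced to ≤ 10 mg prednisone or equivalent per day within 12 weeks".

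**Section 5.5** has an exception to its 5-week interruption limit: "Participants being tapered after high dose corticosteroids over one month followed by a two-week observation period" get two more weeks to restart, with a maximum interruption of eight weeks.

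**Cross-references.** The Section 6 introduction and the opening of 6.2 both cite 5.9 for resuming pembrolizumab, and the text after Table 4.9 cites 5.9 for managing high-dose steroids. Section 5.9 covers infusion reactions. The Table 4.9 footnote cites 5.10 for infusion reactions, but 5.10 is treatment beyond progression.

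**The concern.** Clinicians are likely to use the table when deciding whether to re-dose. Followed as printed, it allows pembrolizumab in someone whom 5.8 still bars: a participant who has just finished steroids, arguably one still on a low dose, or one with residual Grade 1 colitis or a raised liver test that was not present at baseline. Section 5.8 gives its own reason for caution, namely the risk of exacerbation if inflammation remains. The wrong section numbers remove the link that would bring the reader back to the stricter rule. What is at stake is participant safety and uniform conduct across sites, not the efficacy inference.

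**Working it through.** The plan gives no figure to reproduce, so the check compares the texts and does simple timing arithmetic.

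**1. The two rules, for a steroid-treated Grade 2 event**

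| Condition | Section 5.8 | Table 4.1, instruction 2 |
|---|---|---|
| Time off steroids | at least 2 weeks | none stated |
| Four named events | Grade 0 or baseline | Grade 1 or 0 |
| Recurrence or new event | none in those 2 weeks | not mentioned |

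**2. Earliest restart, counted from improvement to Grade 1 or less**

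- Table 4.1: a taper of at least 4 weeks, so about 4 weeks. This takes *tapered* to mean that the taper is complete.
- Section 5.8: 4 + 2 = about 6 weeks.
- Section 5.5, as a check on intent: one month (about 4) + 2 observation + 2 to restart = 8 weeks, its stated maximum. That sum contains the two-week period, so 5.5 agrees with 5.8.

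**3. Whether another rule closes the gap**

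- Section 5.2.3: "Any non-hematologic toxicities must return to baseline or to" below Grade 2 on Day 1, and ALT/AST must be below 2.5 x ULN without liver metastases. No steroid-free interval is given. Appendix B puts Grade 1 ALT/AST at above 1.0 to 3.0 x ULN. With a normal baseline, a value above 1.0 and below 2.5 x ULN therefore passes Table 4.1 and 5.2.3 but fails 5.8. Appendix B is labelled CTCAE v4 and Table 4.1 uses v5.0; the residual Grade 1 colitis example does not depend on that band.
- Section 5.4.1 allows 10 mg prednisone daily during treatment.
- The two-week observation after Table 4.9 applies only to participants found not to need steroids for an autoimmune event.
- The gastrointestinal and hepatic algorithms in Appendix B say to resume per protocol, which leads back to the same two rules.

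**4. Rows affected**

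Table 4.1 has ten event rows. In seven of them a Grade 2 event can lead to both withholding and steroids. Two of the seven are settled elsewhere: Grade 2 pneumonitis needing steroids stops under 5.5, and Grade 2 hypophysitis falls under the hypopituitarism sentence in 5.8. The endocrinopathy note under Table 4.1 covers only Grades 3 and 4, so it does not settle hypophysitis. That leaves 7 - 2 = 5 clearly affected: colitis, liver tests, nephritis, myocarditis, and all other immune-related events.

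**5. The time limits run on different clocks**

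Instruction 2 gives the event 12 weeks from the last dose to resolve. Section 5.8 says "For participants treated with high dose steroids with pembrolizumab, toxicity must resolve to baseline within 8 weeks of treatment", which limits resolution rather than restart. The text after Table 4.9 limits delay: "If treatment is delayed >8 weeks for an adverse event, the participant must be permanently discontinued from study therapy". With a 3-week cycle, and delay counted from the first missed dose:

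- an 8-week delay ends 3 + 8 = 11 weeks after the last dose, so it differs from the table's limit by 12 - 11 = 1 week;
- a limit of 8 weeks from the last dose would leave a delay of only 8 - 3 = 5 weeks, less than the 6 weeks of taper plus steroid-free interval.

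**6. How many participants**

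Section 2.6 reports the same regimen in breast cancer: colitis and renal failure each under 4% and diarrhea 29.9%, all grades. It gives no rate of steroid-treated Grade 2 events, so a count cannot be derived.

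**The case against.** The best reply is that the table is incomplete rather than contradictory. It is headed as guidelines and its wording is permissive, while 5.8 is headed as criteria and addresses everyone treated with steroids. A site that meets 5.8 also meets the table's restart condition, and the wrong pointers miss by a single section. It is true that both rules can be followed together, so a reader should not infer that the plan is unworkable. But no order of precedence is stated, the table says that pembrolizumab may be resumed, and its reader is directed to a section with no resumption rule.

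Three stronger readings are tempting and are not supported:

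- *A grade conflict for every event.* Section 5.8 prints a threshold below Grade 1 where the table accepts Grade 1. This may be a misprint for Grade 1 or less, and 5.8 elsewhere accepts baseline. The point rests on the two weeks and on the separate rule for four named events.
- *A four-week contradiction between 12 and 8 weeks.* The limits start at different times and cover different things. Counted from the first missed dose, the gap is about one week.
- *A separate pancreatitis problem.* Table 4.4 already deals with asymptomatic enzyme elevation and stops pembrolizumab for symptomatic disease, so almost no case is left over.

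**Conclusion.** The inconsistency is real but minor. For steroid-treated Grade 2 immune-related events in five rows, Table 4.1 permits restart about 2 weeks earlier than 5.8, and after colitis or hepatitis at a Grade 1 level that 5.8 rejects unless it was the baseline. Section 5.5 shows that 5.8 is the intended rule. The 4- and 6-week figures assume the minimum taper and that *tapered* means completed; if a low dose may continue, the table is looser still.

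The number affected is probably small. A reader might infer a threat to the efficacy result, but the sample size and the 12-week test do not change. Long-term follow-up ended with the 15 May 2024 version, and the documents do not say whether anyone still receives pembrolizumab. If nobody does, the prospective benefit of a correction shrinks.

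**What to change.** 1. In the Section 6 introduction, the opening of 6.2 and the text after Table 4.9, change the 5.9 references for resumption and steroid management to 5.8. In the Table 4.9 footnote, change 5.10 to 5.9.
2. Add to Table 4.1 instruction 2 that resumption after steroid treatment of an immune-related event must also meet Section 5.8. Keep the thyroiditis and hypopituitarism sentence in 5.8, the Grade 3-4 endocrinopathy note under Table 4.1, and the exceptions after Table 4.9 for short steroid tapers (infusion reaction, skin rash, endocrine events).
3. Leave the 12 weeks from last dose in place. Add that the 8-week maximum delay in 5.5 and after Table 4.9 also applies, counted from the first missed dose, or about 11 weeks from the last dose. The documents speak of interruption and delay without naming a starting point, so this wording would also settle the clock.

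The cost is a wording amendment with no change to sample size or analysis. Restart moves about 2 weeks later. On the first-missed-dose clock, a participant who improves u weeks after that dose could restart at u + 6 instead of u + 4. Against an 8-week limit, those with u above 2 and up to 4 would lose a restart that the table's timing allowed. This assumes that they fall under the high-dose taper exception in 5.5 rather than its general 5-week limit. Section 5.3.4 lets them continue eribulin alone.

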5.9 Treatment of Pembrolizumab Related Infusion Reactions

Since pembrolizumab contains only human immunoglobulin protein sequences, it is unlikely to be immunogenic and induce infusion or hypersensitivity reactions. However, in rare cases, Pembrolizumab may cause severe or life-threatening infusion-reactions including severe hypersensitivity or anaphylaxis. Signs and symptoms usually develop during or shortly after drug infusion and generally resolve completely within 24 hours of completion of infusion. However, if such a reaction were to occur, it might manifest with fever, chills, rigors, headache, rash, urticaria, angioedema, pruritus, arthralgias, hypo- or hypertension, bronchospasm, or other symptoms.

All Grade 3 or 4 infusion reactions should be reported as an SAE if criteria are met. Infusion reactions should be graded according to NCI CTCAE version 5.0 guidelines.

Treatment recommendations are provided below and may be modified based on local treatment standards and guidelines as medically appropriate:

For Grade 1 symptoms: (Mild reaction; infusion interruption not indicated; intervention not indicated)

Remain at bedside and monitor participant until recovery from symptoms. Infusion rate may be slowed. If the infusion is interrupted, then restart the infusion at 50% of the original infusion rate when symptoms resolve; if no further complications ensue after 30 minutes, the rate may be increased to 100% of the original infusion rate. Monitor participant closely.

The following prophylactic pre-medications are recommended for future infusions:

diphenhydramine 50 mg (or equivalent) and/or paracetamol 325 to 1000 mg (acetaminophen) at least 30 minutes before additional pembrolizumab administrations, slowing infusion rate as above.

For Grade 2 symptoms: (Moderate reaction requires therapy or infusion interruption but responds promptly to symptomatic treatment [*e.g.*, antihistamines, non-steroidal anti-inflammatory drugs, narcotics, corticosteroids, bronchodilators, IV fluids]; close observation for recurrence and treatment medications may need to be continued for 24-48 hours).

Stop the pembrolizumab infusion, begin an IV infusion of normal saline, and treat the participant with diphenhydramine 50 mg IV (or equivalent) and/or paracetamol 325 to 1000 mg (acetaminophen); remain at bedside and monitor participant until resolution of symptoms. Corticosteroid or bronchodilator therapy may also be administered as appropriate. If symptoms resolve within 1 hour of stopping drug infusion, the infusion may be restarted at 50% of the original infusion rate (*e.g.* from 100 mL/hr to 50 mL/hr). Otherwise dosing will be held until symptoms resolve and the participant should be premedicated for the next scheduled dose. If the infusion was interrupted, then restart the infusion at 50% of the original infusion rate when symptoms resolve; if no further complications ensue after 30 minutes, the rate may be increased to 100% of the original infusion rate. Monitor participant closely. If symptoms recur, then no further pembrolizumab will be administered at that visit. Administer diphenhydramine 50 mg IV, and remain at bedside and monitor the participant until resolution of symptoms. The amount of study drug infused must be recorded on the electronic case report form (eCRF). The following prophylactic pre-medications are recommended for future infusions: diphenhydramine 50 mg (or equivalent) and (acetaminophen) (or paracetamol) 325 to 1000 mg should be administered at least 30 minutes before additional pembrolizumab administrations. If necessary, corticosteroids (recommended dose: up to 25 mg of IV hydrocortisone or equivalent) may be used.

For Grade 3 or Grade 4 symptoms:

Grade 3 symptoms: (Severe reaction; prolonged [*i.e.*, not rapidly responsive to symptomatic medication and/or brief interruption of infusion]; recurrence of symptoms following initial improvement; hospitalization indicated for other clinical sequelae [*e.g.*, renal impairment, pulmonary infiltrates]).

Grade 4 symptoms: (life threatening; pressor or ventilatory support indicated).

Immediately discontinue infusion of pembrolizumab. Begin an IV infusion of normal saline, and treat the participant as follows: Recommend bronchodilators, epinephrine 0.2 to 1 mg of a 1:1,000 solution for subcutaneous administration or 0.1 to 0.25 mg of a 1:10,000 solution injected slowly for IV administration, and/or diphenhydramine 50 mg IV with methylprednisolone 100 mg IV (or equivalent), as needed. Participant should be monitored until the investigator is comfortable that the symptoms will not recur. Pembrolizumab will be permanently discontinued. Investigators should follow their institutional guidelines for the treatment of anaphylaxis. Remain at bedside and monitor participant until recovery from symptoms. In the case of late-occurring hypersensitivity symptoms (*e.g.*, appearance of a localized or generalized pruritus within 1 week after treatment), symptomatic treatment may be given (*e.g.*, oral antihistamine, or corticosteroids).

Please note that late occurring events including isolated fever and fatigue may represent the presentation of systemic inflammation. Please evaluate accordingly.

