Grade 2 Requires therapy or infusion interruption but responds promptly to symptomatic treatment (e.g., antihistamines, NSAIDs, narcotics, IV fluids); prophylactic medications indicated for ≤24 hrs	
Stop Infusion. Additional appropriate medical therapy may include but is not limited to: IV fluids Antihistamines NSAIDs Acetaminophen Narcotics Increase monitoring of vital signs as medically indicated until the participant is deemed medically stable in the opinion of the investigator. If symptoms resolve within 1 hour of stopping drug infusion, the infusion may be restarted at 50% of the original infusion rate (e.g. from 100 mL/hr to 50 mL/hr). Otherwise dosing will be held until symptoms resolve and the participant should be premedicated for the next scheduled dose. Participants who develop Grade 2 toxicity despite adequate premedication should be permanently discontinued from further study drug treatment
	Participant may be premedicated 1.5h (± 30 minutes) prior to infusion of _____ with: Diphenhydramine 50 mg po (or equivalent dose of antihistamine). Acetaminophen 500-1000 mg po (or equivalent dose of analgesic).
Grades 3 or 4 Grade 3: Prolonged (i.e., not rapidly responsive to symptomatic medication and/or brief interruption of infusion); recurrence of symptoms following initial improvement; hospitalization indicated for other clinical sequelae (e.g., renal impairment, pulmonary infiltrates) Grade 4: Life-threatening; pressor or ventilatory support indicated	
Stop Infusion. Additional appropriate medical therapy may include but is not limited to: Epinephrine** IV fluids Antihistamines NSAIDs Acetaminophen Narcotics Oxygen Pressors Corticosteroids Increase monitoring of vital signs as medically indicated until the participant is deemed medically stable in the opinion of the investigator. Hospitalization may be indicated. **In cases of anaphylaxis, epinephrine should be used immediately. Participant is permanently discontinued from further study drug treatment.
	No subsequent dosing

Appropriate resuscitation equipment should be available at the bedside and a physician readily available during the period of drug administration. For further information, please refer to the Common Terminology Criteria for Adverse Events v5.0 (CTCAE) at http://ctep.cancer.gov
		

Table 4.9 Pembrolizumab dose delay for fever

Fever	Management/Next Dose for Pembrolizumab
≤ Grade 1	Evaluate and continue at same dose level

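### Section 5.9 withholds pembrolizumab only for the current visit when an infusion reaction recurs after restart, although the protocol defines such recurrence as Grade 3 with a permanent stop

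*Combined protocol and SAP*

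**What the plan says.** Section 5.9 sets out the handling of pembrolizumab infusion reactions by grade. It requires that "Infusion reactions should be graded according to NCI CTCAE version 5.0 guidelines" and says its treatment recommendations "may be modified based on local treatment standards and guidelines as medically appropriate".

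- **Grade 2 in 5.9.** Stop the infusion and treat. If symptoms clear within an hour, the infusion may restart at half the original rate. Then: "If symptoms recur, then no further pembrolizumab will be administered at that visit". The paragraph closes with premedication for future infusions, which "should be administered at least 30 minutes before additional pembrolizumab administrations".
- **Grade 3 in 5.9.** The definition includes "recurrence of symptoms following initial improvement". The action for Grade 3 or 4 is "Pembrolizumab will be permanently discontinued".
- **Table 4.8 in Section 6.2.** The Grade 3 definition contains the same recurrence criterion. The action is "Participant is permanently discontinued from further study drug treatment", and the column for later premedication says there is no further dosing.
- **Section 5.5.** A Grade 3 or 4 drug-related infusion reaction, however long it lasts, is among the reasons for discontinuation.
- **Grade 1.** Section 5.9 recommends diphenhydramine and/or acetaminophen before later infusions. Table 4.8 enters None. Table 1 says premedication is not routinely needed except after a previous infusion reaction, and its footnote allows institutional standards.

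**The concern.** A participant reacts, improves when the infusion is stopped, is restarted, and reacts again. The Grade 2 paragraph of 5.9 answers this case directly: no more drug today, then premedicate next time. The Grade 3 definition a few lines later describes the same sequence and ends pembrolizumab for good. Nothing in 5.9 links the two or says that the second reaction must be regraded before the next dose is scheduled.

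What is at stake is re-exposure. Section 5.9 itself warns that pembrolizumab can, rarely, cause severe or life-threatening reactions, including anaphylaxis. A nurse or investigator who follows the recurrence sentence as written could re-dose someone whom the protocol's own definition says should not be re-dosed. The Grade 1 mismatch has a milder consequence: whether premedication is advised after a mild reaction depends on which page is consulted.

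**Working it through.** The plan states no figure on this point, so the check is a comparison of texts, followed by one ceiling on the number affected.

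**1. Recurrence after restart**

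| Place | How the event is classed | Action on pembrolizumab |
|---|---|---|
| 5.9, Grade 2 paragraph | Handled inside Grade 2 | Withheld for that visit; premedication described for later doses |
| 5.9, Grade 3 definition and action | Grade 3 | Permanent stop |
| Table 4.8, Grades 3 or 4 | Grade 3 | Permanent stop, no later dosing |
| Table 4.8, Grade 2 | Same half-rate restart; silent on recurrence within the visit | Not addressed |
| 5.5 | Grade 3 or 4 infusion reaction | Discontinuation |

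Restart presupposes that symptoms have resolved, so a recurrence after restart is necessarily a return after improvement. It meets the recurrence criterion in both Grade 3 definitions, and no text exempts it. The first row is therefore out of line with the second, third and fifth.

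**2. Do the cross-references settle it?** Sections 5.1 and 6 send dose modifications to the Section 6 tables, which points to Table 4.8. But Section 6 also refers to 5.9 for resuming pembrolizumab after a delay, and 6.2 does the same. These references probably mean 5.8, which covers resumption, yet as printed they lead to the section with the conflicting sentence. The note closing Table 4.9 sends infusion reactions to 5.10, which is about treatment beyond progression. The cross-references do not resolve the conflict.

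**3. Grade 1 premedication.** Section 5.9 recommends it, Table 4.8 says None, and Table 1 agrees with 5.9. The Table 4.8 entry is the odd one out.

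**4. Ceiling on the number affected**

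- Input: infusion-related reactions of any grade in fewer than 4% of participants in the earlier combination trial in breast cancer (Section 2.6).
- Input: 57 participants planned (Section 13.2, Table 10).
- Assumption: the same rate applies here.
- Expected number with any infusion reaction < 57 × 0.04 = 2.28.

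The recurrence conflict needs a Grade 2 reaction, a same-visit restart and a recurrence. The documents give no rate for that sequence, so it cannot be quantified further.

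**The case against.** The best defence is that there is no real contradiction. The recurrence sentence is a bedside instruction for the day. It does not say that the participant may have the next dose, and the premedication advice closes the whole Grade 2 paragraph, so it also serves participants who restarted without trouble. CTCAE grading is required, a recurrence is an infusion reaction, and once it is graded 3 three provisions stop treatment. The Grade 3 text in 5.9 also opens by describing a severe reaction, so a mild recurrence might not qualify.

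Part of this stands. A careful investigator can regrade and reach the right answer, so it would be wrong to infer that the protocol lacks a stop rule. But the one sentence that names the event keeps it in the Grade 2 pathway, and regrading is left to be inferred. The severity qualifier is absent from the Table 4.8 row. The local-standards clause covers treatment recommendations and does not clearly reach a permanent stop that 5.9 and Table 4.8 state without exception.

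The defence is stronger on Grade 1. The 5.9 text is only a recommendation, and both it and the Table 1 footnote defer to local or institutional practice. That is a mismatch to tidy, not a hard contradiction.

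Two wider readings are tempting and should not be adopted:

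- A reader might infer that 5.9 conflicts with Table 4.8 because it omits the rule that "Participants who develop Grade 2 toxicity despite adequate premedication should be permanently discontinued from further study drug treatment". That is an omission, and Table 4.8 already supplies the rule through Section 6.
- A reader might infer from the table's reference to study drug that eribulin must stop too. The table's title concerns pembrolizumab. Whether eribulin may continue is a general discontinuation question, separate from recurrence.

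**Conclusion.** The recurrence sentence in 5.9 is wrong as written: it can lead to re-dosing a participant who meets the protocol's own definition for permanent discontinuation. It should be corrected. The Grade 1 entry in Table 4.8 is a minor companion point.

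The size is small. Fewer than 2.3 of 57 participants would be expected to have any infusion reaction, on the assumption that the earlier trial's rate carries over, and the recurrence conflict concerns an unquantified subset of them. This is a safety-conduct inconsistency. A reader might infer an effect on efficacy, but the documents do not support one: Section 13.1 does not count stopping pembrolizumab as a failure on the 12-week primary endpoint, and sample size, type I error and power are unaffected. Urgency depends on whether anyone is still being dosed. The current version ends long-term follow-up, but the documents do not say whether treatment continues.

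**What to change.** 1. In the Grade 2 paragraph of 5.9, amend the recurrence sentence to say that recurrence after restart is graded by the stated Grade 3 definition, that pembrolizumab is then permanently discontinued, and that Table 4.8 governs stopping.
2. In the Grade 1 row of Table 4.8, replace None with the premedication recommended in 5.9, in line with Table 1, and keep the local-standards clause.

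The cost is protocol wording only. No procedures, visits or data are added.
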